## 3 Study Design and Methodology

### 3.1 Study Overview

This is a retrospective cross-sectional comparative study.

Data from private hospital records were accessed and analysed retrospectively.

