### 3.3 Study Population

All refractive surgery candidates attending the above hospital for the purpose of phakic introcular lens implantation were included in the study. However, the initial group allocation occurred before the commencement of the study on the basis of surgeon and patient preference, thereby, randomization was on convenient basis.

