## **3.4 Identification and Recruitment of Participants**

Potential participants will be identified by screening of all medical records from the above hospital regardless of the time of the surgery.

Study investigators will identify study participants individually after screening of medical records.

Since this study is retrospective, initial surgery consent was considered as the participant consent for the study.

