## **3.5 Study Interventions / Procedures**

After enrolment, the record of each participant is examined meticulously for completeness of preoperative and postoperative data pertaining to study including:

Patient age and gender, date of the procedure and its operative notes including laterality and surgical steps.

preoperative and postoperative assessments such as uncorrected and best corrected visual acuity, refractive error quantification both objectively utilizing an autorefractometer autorefractor Nidek ARK 1 (Nidek Inc, Gamagori, Japan) and subjectively as manifest refraction, clinical slit-lamp examination notes, intraocular pressure with air puff tonometers, AC depth assessment by Pentacam Scheimpflug (Oculus Optikgeräte GmbH Inc., Wetzlar, Germany), specular microscopy study of corneal endothelial cells (endothelial cell density (ECD), coefficient of variation (CV) and hexagonality) using Topcon SP-1p Specular Microscope (Topcon Corporation, Tokyo, Japan),

Typically, there is a preoperative visit and multiple postoperative visits extending over the period of 1-2 years after the procedure.

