## 2- Reduced OVD group

In this group of patients, the ICL was implanted with the use of cohesive OVD only.

There is one primary outcome of interest which is the unaided visual acuity after the surgery, and several secondary outcomes including postoperative intraocular pressure, corneal specular microscopy parameters (ECD, CV and hexagonality), and the observed adverse events that can happen during the operation or postoperatively.

Data will then be stored electronically in a sheet format to enable for later statistical analysis.

Data collection was started at the conduct of the study in March 2024, and it is expected to be completed 3-4 months later.

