### 4.2 Statistical methods

After collection of data from patients records and its subjection to thorough analysis for incompleteness and exclusion criteria, these data will be stored electronically in sheet formats for later analysis. All statistical test and subsequent analyses will be performed using SPSS version 26 (IBM statistical software). Data will be classified into categorical and numerical. Categorical variables were described using frequencies and percentages and were analysed using Chi-squared test. Numerical variables, described as mean  $\pm$  standard deviation, will be subjected to tests of normality to determine the appropriate statistical tests for inter- and intra-group comparisons. Unpaired t test or Mann-Whitney test was used to compare the two groups (traditional and modified OVD) according to fulfilled statistical assumptions. These two groups were compared for statistically significant difference regarding all parameters that were collected as per section 3.5 of this protocol. These statistical comparisons were made both preoperatively to determine baseline characteristics of the study participants and postoperatively to determine any significant difference between the two groups. Within the same group whether traditional or reduced OVD, all of the aforementioned parameters were compared again pre- and postoperatively this time using either one sample paired t test or Wilcoxon signed-rank test according to fulfilled statistical assumptions. Significance was considered at P value less than 0.05.

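### Technique was chosen by surgeon and patient preference, with no limit on surgery date, yet the groups are compared only with unadjusted tests, so baseline, case-mix, surgeon or era differences cannot be separated from an OVD effect

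*Combined protocol and SAP*

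**What the plan says.** The design is stated in Section 3.1: "This is a retrospective cross-sectional comparative study". Section 3.3 says the groups were formed before the study "on the basis of surgeon and patient preference, thereby, randomization was on convenient basis". No random process is described. Section 3.4 identifies patients by "screening of all medical records from the above hospital regardless of the time of the surgery".

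Section 3.5 lists the data to abstract: age, gender, preoperative and postoperative acuity, refraction, IOP, anterior chamber depth and specular microscopy, and also "date of the procedure and its operative notes including laterality and surgical steps". Surgeon identity is not named as a field.

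Section 3.6 sets the endpoint: "There is one primary outcome of interest which is the unaided visual acuity after the surgery". IOP, the endothelial parameters and adverse events are secondary.

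Section 4.2 holds the whole analysis plan. For numerical variables: "Unpaired t test or Mann-Whitney test was used to compare the two groups (traditional and modified OVD) according to fulfilled statistical assumptions". For the rest: "Categorical variables were described using frequencies and percentages and were analysed using Chi-squared test". The between-group comparisons are "made both preoperatively to determine baseline characteristics of the study participants and postoperatively to determine any significant difference between the two groups". Paired tests are added within each group. The plan says nothing about what happens if the groups differ at baseline.

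**The concern.** Section 2 asks whether leaving out the dispersive agent is safe and suitable. The contrast between the two groups is the comparative evidence for the answer. When surgeon and patient choose the technique, the choice can follow refraction, anatomy, surgeon habit or calendar period, and each of these may also bear on the outcome. An unadjusted test attributes the whole postoperative difference to technique.

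The error can go either way. A harmless technique could look worse, or a real loss of endothelial cells could be masked by a more favourable starting point. The bias does not shrink as more records are added. A larger sample only makes a wrong answer look more precise.

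**Working it through.** **What the plan allows.** The documents give no sample size, effect size or SD, so there is no planned figure to reproduce. The structural check is to set the sections side by side. Allocation is by preference (3.3), there is no date window (3.4), preoperative values, age and procedure date are collected (3.5), and none of these enters the between-group test (4.2). The paired tests in 4.2 work inside each group and do not adjust the contrast between groups.

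**Illustration of size. All inputs are assumed:**
- two equal groups of n = 50 or n = 100;
- a true baseline gap of d = 0.3 SD;
- no technique effect;
- within-group correlation r between preoperative and postoperative values: 0.6 to 0.8 as might apply to ECD or IOP, and 0.3 as a lower value that may be nearer unaided acuity;
- bivariate normal data and a two-sided 5% test (4.2 gives 0.05 without stating sidedness).

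**Step 1: bias of the unadjusted difference.** Bias = r × d outcome SDs: 0.3 × 0.3 = 0.09, 0.6 × 0.3 = 0.18 and 0.8 × 0.3 = 0.24.

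**Step 2: false-positive rate.** The t statistic has noncentrality r × d × √(n/2), where √(50/2) = 5 and √(100/2) = 7.07.

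| r | n = 50: noncentrality | rejects | n = 100: noncentrality | rejects |
|---|---|---|---|---|
| 0.3 | 0.45 | 7.3% | 0.64 | 9.7% |
| 0.6 | 0.90 | 14.5% | 1.27 | 24.5% |
| 0.8 | 1.20 | 22.1% | 1.70 | 39.3% |

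**Step 3: does the planned baseline test protect?** Its noncentrality is 0.3 × 5 = 1.50 or 0.3 × 7.07 = 2.12. It therefore reaches p < 0.05 in only 31.8% (n = 50) or 56.0% (n = 100) of studies. Simulation (40,000 runs per case) splits the postoperative rejections by the baseline result:

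| | n = 50 (r = 0.6, 0.8) | n = 100 (r = 0.6, 0.8) |
|---|---|---|
| Rejects, baseline test significant | 32.7%, 55.6% | 37.9%, 63.0% |
| Rejects, baseline test not significant | 6.5%, 6.7% | 7.7%, 8.6% |
| Share of all rejections with baseline significant | 70%, 79% | 86%, 90% |

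Most of the excess falls where the baseline table would show the problem, and there the plan specifies no response.

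**Step 4: after adjustment.** ANCOVA on the baseline value rejects in 4.9% to 5.2% of runs over all cases, including r = 0.3. This is expected, because the only confounder simulated is the one in the model. With a further unmeasured factor (0.3 SD gap, coefficient 0.3, baseline r = 0.6; also assumed), baseline-adjusted ANCOVA rejects about 8% at n = 50 and 12% at n = 100.

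**Step 5: precision.** The variance of the technique effect relative to the unadjusted analysis is (1 − r²)/(1 − R²). Here R is the multiple correlation of surgeon and date with technique, and these two are assumed to explain no further outcome variance.

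| R | r = 0.6 | r = 0.8 |
|---|---|---|
| 0 | 0.64/1 = 0.64 | 0.36/1 = 0.36 |
| 0.5 | 0.64/0.75 = 0.85 | 0.36/0.75 = 0.48 |
| 0.7 | 0.64/0.51 = 1.25 | 0.36/0.51 = 0.71 |

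Break-even is at R = r, so a gain in precision is not guaranteed.

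**The case against.** The strongest reply has five parts.

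- **No imbalance is shown.** The documents do not say that the groups differ, or that more than one surgeon operated. The age range and exclusions in Section 3.3 also narrow the case mix. This is correct, and the point is limited to what the plan cannot rule out. But restricting the population does not balance the groups within it.
- **The baseline table would alert readers.** Often it would, as the split of rejections shows. It reveals a measured gap without removing it from the result, and the plan is silent at that stage.
- **The larger percentages belong to secondary outcomes.** This stands. If r is near 0.3 for unaided acuity, the inflation is modest. All the inputs are assumed, and 4.2 itself anticipates non-normal data.
- **Adjustment is not a cure.** This also stands. The return to about 5% holds only when the confounders are measured and correctly modelled, and an unmeasured factor leaves some excess.
- **Surgeon may be in the operative notes.** Section 3.5 does not give an exhaustive list of their contents, so surgeon may well be retrievable. It still has to be made a field and used.

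The visit at which the outcome is taken, and the handling of two eyes from one patient, also need settling. They are separate questions and do not weaken this one.

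**Conclusion.** The concern holds. Followed exactly, the plan could report a difference in baseline, case mix, surgeon or period as an effect of technique, or let such a difference conceal one. Under the assumed 0.3 SD gap, the false-positive rate is roughly three to eight times the nominal 5% for strongly tracking outcomes (14% to 39%), and one and a half to two times for a weakly tracking one (7% to 10%). These figures rest on assumed gap, correlations and group sizes, and show scale only. The absence of any adjustment rests on the text of the plan alone. It affects the primary outcome and every secondary between-group comparison, and should be corrected before the analysis is run.

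**What to change.** **In Section 4.2:**
- Make the main between-group result for each numerical outcome an adjusted difference with a 95% CI. Use ANCOVA with technique, the preoperative value of the same variable, age and surgery date. For unaided acuity, use preoperative best-corrected acuity and refraction as the baseline terms.
- Fix the covariates in advance, whatever the baseline p-values show.
- Where normality fails, use a transformation, rank-based ANCOVA, or a robust or bootstrap CI.
- Report adverse events as a risk difference with a 95% CI, adjusted only if event counts allow.
- Report baseline balance as standardised differences.
- Keep the t, Mann-Whitney and Chi-squared tests as supportive.
- Add a sensitivity analysis restricted to the period when both techniques were in use.
- If surgeon or period fully determines technique, state that the effects cannot be separated.

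**In Section 3.5:** add surgeon, taken from the operative notes where recorded, and adjust for it where surgeons used both techniques.

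**In Section 3.3:** describe the allocation as non-randomised, by surgeon and patient preference. This corrects wording only, since the sentence already gives the true basis.

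**Cost:** revised plan text and a few SPSS GLM commands. Preoperative values, age and procedure date are already collected. Surgeon may need extra abstraction and may be missing for some cases. Unmeasured confounding remains, the CI can widen if surgeon or date tracks technique closely, and rare events may not support adjustment.

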### **Inclusion Criteria**

Refractive surgery candidates

Aged from 18-55 years

Phakic intraocular lens implantation was performed (ICL type)

Committing to at least one preoperative visit for baseline assessment and multiple postoperative visits (at least 2 visits within a year) for follow-up assessment.

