## **3.6 Data collection and analysis**

Data will be collected by study co-investigators with assistance from IT personnel at the respective hospital from patients records that were identified as eligible for the study according to the inclusion criteria above. According to their data, participants will be split into two groups:

1- Traditional OVD group

In this group of patients, the ICL was implanted utilizing both cohesive and dispersive ophthalmic viscosurgical device.

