### 3.7 Handling of Missing Data

Section 3.5 of this protocol defines the data sets that will be collected from patients. Any missing information in this regard would be considered as incomplete data and this will meet an exclusion criterion and thereby a participant would be totally excluded from the study even if all other parameters are present.

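### Section 4.2 has no rule for two operated eyes of one patient, although every planned test needs independent units

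*Combined protocol and SAP*

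**What the plan says.** Section 4.2 sets the tests. For numerical variables between groups: "Unpaired t test or Mann-Whitney test was used to compare the two groups (traditional and modified OVD) according to fulfilled statistical assumptions". On scope: "These two groups were compared for statistically significant difference regarding all parameters that were collected as per section 3.5 of this protocol". Pre/post comparisons within a group are made "using either one sample paired t test or Wilcoxon signed-rank test according to fulfilled statistical assumptions". Categorical variables get a Chi-squared test, and the threshold is P below 0.05.

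Section 3.5 lists the parameters. Age and gender belong to the patient. Refraction, slit-lamp findings, intraocular pressure, anterior chamber depth, endothelial cell density, coefficient of variation and hexagonality belong to an eye. The extraction also covers "date of the procedure and its operative notes including laterality and surgical steps", so the data sheet could tell eyes apart, but section 4.2 makes no use of this.

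Sections 3.6 and 3.7 speak of people. On grouping: "According to their data, participants will be split into two groups". On any missing item: "a participant would be totally excluded from the study even if all other parameters are present". Section 3.6 also states: "There is one primary outcome of interest which is the unaided visual acuity after the surgery". It does not say whether acuity is taken in one eye or both.

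Section 3.3 and the eligibility lists neither restrict the study to one eye per patient nor exclude patients operated on in both. No section defines the unit of analysis.

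**The concern.** All five planned tests treat each entry as an independent observation. Two eyes of one person tend to resemble each other, so the second eye adds less than a full observation. The paired tests do not solve this: they pair before with after, not one eye with its fellow.

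The consequence depends on how two-eye patients are entered, which the plan leaves open:

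- **Two rows in the same group.** The standard error is too small. Between-group differences and pre/post changes are declared significant too often.
- **One row in each group.** The unpaired test ignores the link between the two eyes and becomes conservative.
- **One value per patient.** The tests hold, but which eye supplies the value is not fixed and could be settled after the results are seen.

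**Working it through.** **Inputs.** The only numerical input in the documents is the 0.05 threshold in section 4.2. Sidedness is not stated, so two-sided is assumed. Section 4.1 gives no sample size or power, so there is no figure of the plan's own to reproduce. Two quantities must be assumed:

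- *b*, the share of patients with both eyes operated: 0.25, 0.5 or 1.
- *rho*, the correlation between fellow eyes: 0.3 to 0.9. For the pre/post tests this is the correlation of the *change*, which is a different quantity and may lie elsewhere in the range or below it.

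**Fellow eyes as separate rows in the same group.** Take n patients, of whom nb give two eyes, so there are n(1+b) rows with variance s² each.

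- Variance of the sum if rows were independent: n(1+b)s².
- Actual variance: n(1−b)s² + nb·2s²(1+rho) = ns²[(1+b) + 2b·rho].
- The ratio is the design effect: DE = 1 + 2b·rho/(1+b).
- True type I error: 2[1 − Phi(1.96/√DE)].

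Worked case, b = 0.5 and rho = 0.5: DE = 1 + (2 × 0.5 × 0.5)/1.5 = 1.333. Then 1.96/√1.333 = 1.697, and the type I error is 0.090.

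| b | rho 0.3 | rho 0.5 | rho 0.7 | rho 0.9 |
|---|---|---|---|---|
| 0.25: DE | 1.12 | 1.20 | 1.28 | 1.36 |
| 0.25: type I error | 0.064 | 0.074 | 0.083 | 0.093 |
| 0.5: DE | 1.20 | 1.33 | 1.47 | 1.60 |
| 0.5: type I error | 0.074 | 0.090 | 0.106 | 0.121 |
| 1: DE | 1.30 | 1.50 | 1.70 | 1.90 |
| 1: type I error | 0.086 | 0.110 | 0.133 | 0.155 |

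With b = 0, or one value per patient, DE = 1 and the error is 0.05. At rho = 0.1 the error is only about 0.055 (b = 0.25, DE 1.04) to 0.062 (b = 1, DE 1.10).

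**Check by simulation.** Normal data, 30 bilateral patients (60 eyes) per group, 10,000 runs, rho 0.3, 0.5, 0.7, 0.9:

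- unpaired t: 0.086, 0.111, 0.138, 0.159
- Mann-Whitney: 0.085, 0.109, 0.136, 0.154
- paired t on change: 0.088, 0.108, 0.131, 0.155

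These agree with the formula for b = 1.

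**Fellow eyes in opposite groups.** If every patient has one eye in each group, the variance of the difference is multiplied by (1 − rho). The true type I error of the unpaired test is 2[1 − Phi(1.96/√(1−rho))]. At rho = 0.3, 1.96/√0.7 = 2.343, giving about 0.019. At rho = 0.5 it is about 0.006, and at 0.7 or more it is below 0.001.

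**The case against.** The strongest reply is that the plan means one value per patient. It groups participants, describes each group as patients and excludes whole participants, and it never calls an eye a row or a unit. That is a plausible reading, and under it the tests keep their 5% level. What remains is narrower: nothing says how a patient with two operated eyes gives one pressure or one cell density.

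It can also be said that section 4.2 makes the choice of test depend on assumptions being met. That clause, read with the normality tests, only chooses between a t test and a rank test. Both need independence, so no listed option handles fellow eyes.

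The size is wholly assumed, and that objection stands. Recording laterality does not show that any patient had both eyes operated, and 0.155 needs every patient bilateral with a correlation of 0.9. If acuity is recorded binocularly, the primary outcome is unaffected.

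Two stronger readings are tempting, and the documents do not support either:

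- *A reader might infer that the plan counts eyes as independent.* It does not say so; it is silent.
- *A reader might infer that double counting would make the reduced-OVD technique look safer than it is, through intervals that are too narrow.* Section 4.2 plans means, standard deviations and P-values, and no confidence intervals. Same-group double counting also makes a non-significant result harder to reach, not easier. Taking non-significance as evidence of safety is a separate matter that a two-eye rule does not cure.

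Confounding may well matter more to the conclusions, since section 3.3 describes allocation by preference and the tests are unadjusted. That does not remove this gap.

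**Conclusion.** The omission is certain: the plan permits only independent-unit tests, applies them to mostly per-eye parameters, admits patients with two operated eyes, and gives no rule for them. The harm is conditional. It is nil for the type I error if each patient gives one value, though the choice of eye stays free. With both eyes as rows in the same group, a nominal 5% test runs at roughly 6% to 16% over the assumed grid of bilateral share (a quarter to all) and correlation (0.3 to 0.9), and closer to 5% at lower correlation. The error goes the other way if fellow eyes are split between groups, which grouping by participant makes less likely. The plan should be changed, but the documents do not show that its results will be wrong.

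**What to change.** In section 4.2, name the patient as the independent unit, include operated eyes only, and commit to one of two routes for numerical outcomes and pre/post changes:

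1. **All operated eyes.** A mixed model, or a GEE with a small-sample correction, clustered on patient (SPSS MIXED or GENLIN). This also handles any patient with one eye in each group. The correction matters: in simulations with normal data and assumed groups of 10 to 50 patients, uncorrected GEE gave a type I error of 0.052 to 0.087, corrected GEE 0.047 to 0.062, and a random-intercept model 0.048 to 0.055.
2. **One operated eye per patient.** Keep the planned tests on an eye chosen by a rule fixed before analysis, for example the first-operated eye. In the same simulations this gave 0.047 to 0.052, and it leaves the rank tests available if the data are not normal.

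Analyse categorical outcomes and adverse events by the same one-eye rule or by a binary GEE clustered on patient. Report the number of patients and of eyes in each group.

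The cost is a few sentences and no new data. Route 1 needs a patient identifier, one row per eye and a stated model. Route 2 needs one derived column and gives up the fellow-eye data. P-values will be larger than if eyes were counted as independent. For b from 0.25 to 1, the standard error rises by a factor √DE under route 1, from √1.12 = 1.06 to √1.90 = 1.38 (rho 0.3 to 0.9), and by √(1+b) under route 2, from 1.12 to 1.41.

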## 1 Background

Refractive errors (myopia, hyperopia and astigmatism) are quite prevalent worldwide, they constitute the most common cause of visual impairment with myopia in particular being progressively increasing in its prevalence so that it is predicted that by 2050 nearly half of the world population will be myopic. Management modalities include correction with glasses, contact lenses, laser vision correction, intracorneal implants and intraocular refractive procedures such as phakic intraocular lens (PIOL) implantation which involves the use of implantable collamer lens (ICL) in many cases. PIOLs are being extensively used since they preserve the integrity of the cornea and thereby attaining higher quality of vision compared with conventional kerato-refractive procedures. Furthermore; they allow broader range of refractive errors to be corrected. The Staar V4c EVO visian ICL (Staar surgical Inc, Lake Forest, CA, USA) has demonstrated effectiveness and an excellent safety profile with more than one million ICL implants had already been performed globally. However, complications such as raised intraocular pressure (IOP), cataract and pupillary block do happen. The ICL implantation procedure typically utilizes viscoelastics to facilitate introduction and positioning of the implant. Viscoelastics should be removed thoroughly at the conclusion of the procedure, and failure to do so may induce early postoperative IOP rise. It is logical to assume that viscoelastics use during surgery increases operation cost and time due to the extra steps involving the injection and removal of the substance. Increased manipulation during ICL implantation surgery and irrigation required to ensure adequate removal of viscoelastics may encourage cataract formation as well. Few studies investigated the safety and efficacy of ICL implantation without the use of viscoelastics, where they implemented balanced salt solution (BSS) instead as a novel technique. In the present study we retrospectively investigated the safety and efficacy of modifying ICL implantation technique by using cohesive OVD only without using dispersive OVDs.

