### 4.1 Sample size and statistical power

This study involves a convenient non-probability sample based on the availability of patients records in the respective center for enrolment and analysis.

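### Postoperative IOP is compared only as a numerical variable, so large rises in a minority of eyes could be missed; add a pre-set per-eye proportion, and analyse ECD as change from each eye's own baseline, beside the planned tests

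*Combined protocol and SAP*

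**What the plan says.** The Reduced OVD group part of section 3.6 names unaided visual acuity as the single primary outcome and lists "several secondary outcomes including postoperative intraocular pressure, corneal specular microscopy parameters (ECD, CV and hexagonality" and observed adverse events after it. Section 4.2 describes numerical variables by mean and standard deviation. They "will be subjected to tests of normality to determine the appropriate statistical tests for inter- and intra-group comparisons", and between groups "Unpaired t test or Mann-Whitney test was used to compare the two groups (traditional and modified OVD) according to fulfilled statistical assumptions". The comparison covers everything extracted: "These two groups were compared for statistically significant difference regarding all parameters that were collected as per section 3.5 of this protocol". Within each group, preoperative and postoperative values are compared by paired t or Wilcoxon signed-rank test, but the change is never contrasted between groups. For categories, "Categorical variables were described using frequencies and percentages and were analysed using Chi-squared test".

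No IOP level, IOP rise, percentage ECD loss, proportion of eyes or maximum is defined. Adverse events are not defined either, and section 3.5 does not name them among the parameters extracted. On mechanism, the Background (section 1) says of incomplete viscoelastic removal that "failure to do so may induce early postoperative IOP rise".

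**The concern.** The aim (section 2) is to judge whether dropping the dispersive viscoelastic is safe. A pressure rise from retained viscoelastic would plausibly occur in the eyes where removal was incomplete and leave the others unchanged. Such a pattern moves the group mean little and the ranks even less. It also makes the data visibly non-normal, so the planned rule moves to the test that discards how extreme the affected eyes are. With no planned sample size and no safety margin, a non-significant P value could be read as reassurance even if one technique gave more eyes with a marked rise. The same question arises for ECD, but the reason for weak power there is different, as the working shows.

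**Working it through.** **Inputs from the plan.** Significance level: "Significance was considered at P value less than 0.05" (sidedness not stated; two-sided assumed). Group size: none; "This study involves a convenient non-probability sample based on the availability of patients records". The plan gives no effect size, SD, event rate or power, so there is no figure of its own to reproduce.

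**Assumed inputs.** IOP is normal with mean 14 and SD 2.8 mmHg. A fraction f of eyes in one group gains 12 mmHg. There are 100 independent eyes per group. The normality test is Shapiro-Wilk at 0.05 in each group. The 22 mmHg threshold is only an illustration.

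**Step 1: Mann-Whitney.** An affected eye exceeds an unaffected one with probability Φ(12/(2.8·√2)) = Φ(3.03) = 0.999. With f = 0.08, the chance that an eye from the affected group exceeds one from the other group is 0.92·0.5 + 0.08·0.999 = 0.540. The null standard error is √(201/(12·100·100)) = 0.0409. So z = 0.040/0.0409 = 0.97, and power is P(Z > 1.96 − 0.97), about 16%. The same arithmetic gives about 9% at f = 0.05 and 23% at f = 0.10. Simulation of the full rule (2000 to 3000 runs) gave 10%, 16% and 24%. At f = 0.08 it chose Mann-Whitney in over 99% of runs.

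**Step 2: t test without the switch, f = 0.08.** Mean difference: 0.08·12 = 0.96 mmHg. Variances: 7.84, and 7.84 + 144·0.08·0.92 = 18.44. Standard error: √((7.84 + 18.44)/100) = 0.513. So z = 1.87 and power is about 46%, as in simulation. The switch itself therefore costs power.

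**Step 3: proportion above 22 mmHg, f = 0.08.** An affected eye passes with probability Φ(4/2.8) = 0.923, an unaffected one with 1 − Φ(8/2.8) = 0.002. The group proportions are 0.08·0.923 + 0.92·0.002 = 0.076 and 0.002. Summing exact binomial probabilities over the tables where Fisher's test gives P < 0.05 yields 72%. Simulations gave 71% to 74%.

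**Step 4: how far the gain depends on the assumptions.** The f = 0.08 model is used unless stated.

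| Scenario | Planned rule | Fisher on threshold |
|---|---|---|
| 8% v 0%, 100 per group | 16% | 74% |
| 8% v 2%, 100 per group | 13% | 31% |
| 8% v 0%, rise of 8 mmHg | 17% | 20% |
| 5% v 0%, 60 per group | 8% | 6% |
| 10% v 0%, 40 per group | 13% | 15% |
| Uniform shift of 1.2 mmHg, 100 per group | 85% | 0% |

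Moving the threshold to 25 mmHg at 8% v 0% lowers Fisher to 41%, below a plain t test (48% in that run). A second model (mean 14, SD 2.5; affected eyes mean 32, SD 4; threshold 24), with 10% v 1% affected and 100 per group, gave 21% for the rule, 68% for t and 74% for Fisher. At 20% v 2% the rule reached 60%.

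**Step 5: ECD.** Assumed: mean 2750, SD 300 preoperatively; loss 2% (SD 4%); 8% of eyes in one group lose a further 20%; 100 per group.
- Raw postoperative values: mean difference 0.08·550 = 44 cells. SD in the unaffected group: √((0.98·300)² + 110²) = 314. SD in the affected group: √(314² + 550²·0.08·0.92) = 348. Standard error: √((314² + 348²)/100) = 46.9. So z = 0.94 and power is about 16% (simulated: t 15%, Mann-Whitney 12%).
- Percentage change: difference 0.08·20 = 1.6 points. SDs: 4 and √(16 + 400·0.08·0.92) = 6.74. Standard error: 0.784. So z = 2.04 and power is about 53% (simulated t test: 54%). The proportion losing at least 15% reached 78%.
- Normality of raw ECD was rejected in only about 11% of runs, so the test is not usually switched. Most of the loss comes from between-eye spread.

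**The case against.** The strongest reply has four parts.

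First, adverse events are a secondary outcome and categorical variables get a chi-squared test. The Background lists raised IOP as a complication, so high readings might be counted there. This stands in part: the plan does not look only at averages. But with no definition, whether a high reading counts depends on what was noted in the chart, so the outcome cannot be relied on to capture these eyes.

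Second, that harm sits in a few eyes is an assumption. The Background makes it plausible for IOP but gives no share of eyes, and says nothing of the kind for the endothelium. This stands. For a general shift the planned test works well and a threshold test can fail completely.

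Third, an unaffected comparator is a best case, because both groups receive cohesive viscoelastic and either could have rises. This stands, and it cuts the gain sharply (31% against 13% at 8% v 2%).

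Fourth, the 78% against 15% contrast for ECD is not like for like, since one side uses within-eye loss and the other raw values. This stands.

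A reader might infer that the safety tests are nearly blind to harm, that a falsely reassuring result is likely, or that proportions should replace the mean comparison. The documents support none of these: they give no group sizes, affected share or size of rise, and each choice of test misses a pattern that the other finds.

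**Conclusion.** The gap is real for IOP. The plan sets no per-eye IOP category, and if a minority of eyes has large rises its normality rule leads almost always to a test with about 10% to 25% power, at 100 eyes per group with 5% to 10% affected in one group and none in the other. The advantage of a threshold comparison runs from large (about 74% against 16%) to nil, depending on assumptions that the documents neither state nor exclude.

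For ECD, a reader might carry over the explanation that affected eyes trigger the switch to Mann-Whitney. On raw postoperative values they mostly do not; the weakness is between-eye variation, which change from the eye's own preoperative value removes.

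Because these are secondary outcomes and the size rests on assumed distributions and independent eyes, this is a point that should be fixed, not one on which the study stands or falls. Confidence is medium.

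**What to change.** In sections 3.6 and 4.2, add the following alongside the planned comparisons and not in place of them:

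- **IOP:** the proportion of eyes per group whose postoperative IOP, or rise from the eye's own preoperative value, exceeds a threshold that the investigators fix before comparing the groups.
- **ECD:** percentage change from the eye's own preoperative value, compared between groups, with the proportion of eyes beyond a pre-set loss.

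For each, report the counts, the between-group difference with a confidence interval, an exact test for the proportions, and the maximum IOP and maximum ECD loss per group. Give the mean difference in percentage ECD change with its interval whatever the normality test shows. In the second simulation model, percentage change was affected by the switch much as IOP was (10% v 1% affected, 100 per group: rule 18%, t test 61%).

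The cost is protocol wording and two derived columns in the data sheet; no new data are needed. The downsides are that thresholds must be agreed in advance and that two more secondary comparisons are added. With small groups the proportions will also be imprecise, and the confidence interval will show this where a P value alone would not. The 22 mmHg and 15% used here only illustrate the arithmetic and are not proposals.
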